5.10 Important Protocol Deviations Leading to Exclusion from the PP Analysis

All important and non-important protocol deviations are defined in a separate documentation where each PD's detection methods are indicated by monitoring or programming.

Only those important protocol deviations considered to have a major effect on the primary efficacy endpoint will lead to complete exclusion of the patient from the PPS.

The following criteria have been identified as important protocol deviations leading to exclusion from the PPS as it is considered that the occurrences of any of these criteria might have an important influence on the primary efficacy endpoint.

Note: Emergency unblinding may lead to a patient being removed from PPS even if it is not included as a PD.

Statistical Analysis Plan

Sponsor Name: Poxel
Sponsor Protocol ID: PXL065-003

5.10.1 Failure of Inclusion/Exclusion Criteria

Non-compliance with Inclusion / Exclusion criteria leading to exclusion from PPS will be described in the BDRM minutes.

Per protocol, if a patient who does not meet the inclusion/exclusion criteria mistakenly enters the double-blind treatment period, a discussion should occur between the POXEL Medical Representative, the Medical Monitor and the Investigator regarding whether to continue or discontinue the IMP, based on patient's safety and study's consideration. In situations where an agreement cannot be reached, the patient should be withdrawn from the study. In such case, patients will be considered as withdrawn from the study due to protocol deviation (GCP non-compliance) and may be excluded from PPS.

5.10.2 Prohibited Medications

Prohibited medications leading to exclusion from PPS will be described in the BDRM minutes. Per protocol, patients must not take any of the following licensed medications from the Randomization Visit (V1) up to Week 38 (V9-EoS):

- Any medication containing pioglitazone (e.g. Actos®, Actoplus Met®, Duetact®, Oseni®) or other approved or experimental TZD (e.g. rosiglitazone (Avandia®), leriglitazone (MIN-102), MSDC-0602K), or PPARy agonists
- Any other antidiabetic drug except those permitted in the inclusion criterion #5 (Protocol Section 5.1 Inclusion criteria: Metformin, sitagliptin, alogliptin, empagliflozin, canagliflozin, and dapagliflozin)
- Topiramate
- Amiodarone
- Bile salt chelators
- Methotrexate
- Chronic corticosteroids (> 2 consecutive weeks) with a systemic effect (e.g. oral or intravenous administrations) at doses ≥ 10 mg/day of oral prednisone (or equivalent)
- Equal or more than 800 U of vitamin E per day
- Orlistat
- Obeticholic acid
- Any other medications (including vitamins, herbal and dietary supplements) known to affect liver function/steatosis at the Investigator's discretion

Corporate confidential information

5.10.3 Accidental or Emergency Unblinding During Treatment**Period**

If the treatment code for a patient is inadvertently revealed to one or more site staff or project team members who should have remained blind until database lock, this will lead to patient exclusion from the PPS.

If it becomes necessary for the investigator to unblind a specific patient in an emergency because of a safety concern, this will exclude the patient from the PPS.

5.10.4 Errors in Treatment Allocation During Treatment Period

Some patients may have received the wrong IMP treatment at one or more study visits due to randomization, packaging or dispensing errors.

If the wrong treatment was received at all or most visits, then the patient should be assigned to the actual or predominant treatment received in the PPS analysis at all visits (in contrast to the randomized treatment for the ITTS-w-065-S /ITTS analysis).

If the wrong treatment was received at a single visit, then the patient should be assigned to the randomized treatment in the PPS analysis at all visits, possibly with exclusion of the patient from the PPS if this is considered of sufficient concern for key efficacy conclusions.

Impact of incorrect IMP administration on efficacy analysis will be discussed and decided prior to database lock and unblinding at the BDRM.

5.10.5 Adequate Study Medication Compliance

The acceptable overall compliance will be within 80% - 120% ($\geq 80\% - \leq 120\%$). If at any visit the compliance does not fall within this range, it must be reported as a protocol deviation (if it occurs anytime during treatment period), however, this may not necessarily mean that the patient will be excluded from the PPS and will be reviewed by the study team at the BDRM.

5.10.6 Assessment of Important Protocol Deviations

Important protocol deviations which require clinical or medical monitoring interpretation will be reviewed periodically during the protocol deviations review by the team.

All-important protocol deviations leading to exclusion from the PPS occurring during the study will be reviewed and approved by Poxel prior to unblinding during the BDRM.

Should additional important protocol deviations leading to exclusion from the PPS, not anticipated at the time of preparing this SAP, be identified during the study (and prior to unblinding) they will be documented in a SAP amendment/updated Important Protocol Deviations Designation and Escalation document and included in all relevant protocol deviation reviews and approvals.

Statistical Analysis Plan

Sponsor Name: Poxel
Sponsor Protocol ID: PXL065-003

6. DATA Handling

6.1 Time Points and Visit Windows

Day 1 is defined as the day of randomization. Relative days after Day 1 are calculated as (assessment date – Day 1 date) + 1. Relative days prior to Day 1 are calculated as (assessment date – Day 1 date). The day prior to Day 1 is Day -1.

To maximize the data available for analysis, where possible, results from ET and Unscheduled Visits will be allocated to scheduled visit according to the following rules and visit windows described in Table 2.

- If a valid value exists for the scheduled visit to which the ET/Unscheduled Visit has been allocated then the value from the scheduled visit will be used in the analysis, otherwise the values from the ET/Unscheduled Visits will be used in the analysis for the particular scheduled visit.
- If more than one ET/Unscheduled Visit is allocated to the same scheduled visit (and no valid value from the scheduled visit is available) then the closest visit value will be used in the analysis for the scheduled visit.

Visit Windowing rules are defined according to parameters groups in **Table 1** - **Visit window groups** and the windows in **Table 2**.

Double-blind treatment period is defined as the period between the randomization visit (V1) and the EoT visit (V8). Follow-up period is defined as the period between the EoT visit (V8) and the EoS visit (V9).

Table 1 - Visit window groups

Visit window group	Visits	Parameters
Group 1	All visits	Pitting edema assessment, vital signs and body measurements, physical examination
Group 2	Screening, V1, V4, V6, V8	HbA1c
Group 3	Screening, V1, V4, V6, V8, V9	Safety lab, FPG
Group 4	Screening, V1, V5, V8, V9	ECG
Group 5	Screening, V8	DXA, MRI-PDFF, Liver biopsy
Group 6	Screening, V1, V8	eGFR
Group 7	Screening, V1, V5, V9	Pregnancy test
Group 8	V1, V4, V6, V8	Measured metabolic parameters, insulin resistance indexes
Group 9	V1, V8	Fibrosis biomarkers, biobanking sampling

Statistical Analysis Plan

Sponsor Name: Poxel
Sponsor Protocol ID: PXL065-003

Table 2 - Visit windows

Visits	Study day ^a	Group 1	Group 2	Group 3	Group 4	Group 5	Group 6	Group 7	Group 8	Group 9
Screening	N/A	-∞ to -1	-∞ to -1	-∞ to -1	-∞ to -1	-∞ to -1	-∞ to -1	-∞ to -1		
Randomization	1	1 to 12	1 to 43	1 to 43	1 to 64		1 to 127	1 to 64	1 to 43	1 to 127
Week 3	22	13 to 33								
Week 6	43	34 to 64								
Week 12	85	65 to 106	44 to 127	44 to 127					44 to 127	
Week 18	127	107 to 148			65 to 190			65 to 197		
Week 24	169	149 to 190	128 to 211	128 to 211					128 to 211	
Week 30	211	191 to 232								
Week 36	253	233 to 260	212 to ∞	212 to 260	191 to 260	79 to ∞	128 to ∞		212 to ∞	128 to ∞
Week 38	267	261 to ∞		261 to ∞	261 to ∞			198 to ∞		

^a Relative to the date of randomization (Day 1)

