#### 6.2.1 Double-blind Treatment Period

The double-blind treatment period starts at the time the first IMP dose is taken by the patient, on the day of the Randomization Visit (V1), in the morning, following randomization to one of the 4 double-blind treatment groups in this study.

To ensure a double-blind design, regardless of the treatment group, all patients will take an oral dose of 2 tablets QD of either placebo and/or PXL065 7.5 mg or 15 mg depending on the group they have been allocated to:

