#### 8.3.8.1.4 Adverse Event of Special Interest (AESI)

An AE of Special Interest (AESI, serious or non-serious) is one of scientific and/or medical concern specific to the Sponsor's product or program, for which ongoing monitoring and rapid communication by the investigator to the Sponsor can be appropriate. Such an event might warrant further investigation in order to characterize and understand it. Depending on the nature of the event, rapid communication by the trial Sponsor to other parties (e.g., regulators) might also be warranted.

Even if non-serious, AESI are managed with the same process than SAE:

- notification to the Sponsor within 24h following investigator awareness
- case to be created and processed in the safety database (including narrative writing) by Safety Provider.

In this study, the following AEs are considered as AESI:

- Heart failure. In case of any event of heart failure, whatever the cause, patients should be referred to a cardiology specialist.
- Pitting edema. In case of occurrence of pitting edema with presence of other suspected signs and/or symptoms of heart failure, patients should be referred to a cardiology specialist.
- Bladder cancer
- Bone fracture
- Drug-induced liver injury (DILI)

**Below are specific recommendations for the management of elevated liver transaminases and/ or total bilirubin to detect and monitor a possible DILI, following FDA guidelines:**

- **For patients with normal liver transaminases and total bilirubin at baseline (Randomization Visit (V1)):**

If patients with normal baseline (Randomization Visit (V1)) liver indices develop new elevations of AST or ALT  $>3 \times$  ULN or TBL  $>2 \times$  ULN values during the study, repeat testing should be performed within 48 to 72 hours. Investigators should also ask the patient if he/she has symptoms.

If there are persistent elevations (ALT or AST  $>3 \times$  ULN or TBL  $>2 \times$  ULN) upon repeat testing, then close observation (as described below) should be implemented and discontinuation of drug should be considered.

Drug should be discontinued, and the patient followed until resolution of symptoms or signs in the following situations:

- ALT or AST  $>8 \times$  ULN
- ALT or AST  $>5 \times$  ULN for more than 2 weeks.

- ALT or AST  $>3 \times$  ULN and (TBL  $>2 \times$  ULN or INR  $>1.5$ , except for patients on anticoagulant treatment)

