7.1 General Principles

All data processing, summarization and analyses will be performed using SAS Environment / Version 9.4 (or later) of the SAS® statistical software package.

The following principles will be applied to all tables, figures and listings (TFLs) unless otherwise stated:

Principle	Value
Significant tests	Two-sided and use a 5% significance level for main effect
Treatment group labels and order presented	PXL065 7.5mg QD PXL065 15 mg QD PXL065 22.5mg QD Placebo
Visit labels presented	Tables and Figures: Week XX Listings: Screening Randomization (V1) Week 3 (V2) Week 6 (V3) ... Week 36 (V8-EoT) End of Study (V9-EoS) Early termination Unscheduled
Tables	Data in summary tables presented by treatment group, assessment (where applicable) and analysis visit (where applicable).
Listings	All data collected presented by treatment group, patient, nominal visit, Date unless otherwise specified.
Descriptive summary statistics for continuous variables	Number of patients/observations (N) Mean SD standard error of the mean (SEM), median interquartile range (25 th percentile, 75 th percentile) (Q1, Q3) minimum and maximum
Descriptive summary statistics for categorical variables	Frequency counts and percentages: n (%)
Denominator for percentages	Number of patients in the analysis population, unless stated otherwise in table shell(s).
Include "Missing" as category	Yes, when the number missing is greater than zero for at least one treatment group.

Statistical Analysis Plan

Sponsor Name: Poxel
Sponsor Protocol ID: PXL065-003

Principle	Value
Display for 0 percentages	Leave blank
Display to one more decimal place than collected value	Mean SEM Mean Difference Median Interquartile range (Q1, Q3)
Display to 2 more decimal places than collected value	SD Confidence Intervals (CI)
Limit of precision for displays	3 decimal places
Date Format for the presentation in the listings	DDMMYYYY

The baseline value is defined as last scheduled or unscheduled value collected prior to the first dose of IMP treatment, scheduled on Randomization Visit (V1). Assessments carried out on day of first treatment administration are considered to have taken place before the IMP administration, if the corresponding times have not been recorded.

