7.6.2.3 Other Secondary Continuous Endpoints

Efficacy will be further assessed based on the following secondary continuous endpoints:

- Liver enzymes: ALT, AST, GGT, ALP
- Measured glycemic parameters: FPG, HbA1c, serum insulin, C-peptide
- Insulin resistance indexes: HOMA-IR, QUICKI, HOMA- β , Adipo-IR

The change from baseline (Randomization Visit [V1]) to Week 36 (V8) will be analyzed using a Mixed Model for Repeated Measures (MMRM) for the secondary continuous parameters with fixed effects for treatment, stratification factors, i.e. T2DM status (T2DM patients versus non-T2DM patients) and NASH CRN fibrosis scoring system (F1 versus F2/F3), baseline endpoint specific parameter value, time-point, and treatment by time-point interaction. Covariance parameters will be estimated via the REML method. Compound symmetry will be used for the covariance structure. The Kenward and Roger's method for evaluating the degrees of freedom will also be used. Example SAS code is shown in Appendix C.

All patients in the ITTS with non-missing baseline data and at least one post-baseline data are included in the analysis mode, which uses values at all time points with data available. The MMRM analyses will use observed data only, no imputations of data will be performed.

The LSMS for change from baseline at Week 36 and LSM differences for change from baseline between PXL065 treatment groups and placebo will be presented along with 95% CIs and the comparison p-value. A two-sided nominal significance level of 0.05 will be used for treatment comparison.

In addition, the results and changes from baseline at scheduled visits will be summarized by treatment group and visit using standard descriptive statistics for the ITTS.

The same statistical analyses described above will be repeated for the ITTS-w-065-S for the following secondary continuous endpoints:

- Liver enzymes: ALT, AST

CONFIDENTIAL

Statistical Analysis Plan

Sponsor Name: Poxel
Sponsor Protocol ID: PXL065-003

- Measured glycemic parameters: FPG, HbA1c

A listing of secondary continuous efficacy endpoint data will be produced for the ITT set with site 065-S .

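### SAP Table 2 extends the Randomization window past the first dose, so early-termination labs up to Day 43 and ECGs up to Day 64 drop out of the by-visit analyses

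*SAP*

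**What the plan says.** SAP 6.1 sets the day count: "Day 1 is defined as the day of randomization". Protocol 6.2.1 places the start of dosing on that same day, the "first IMP dose is taken by the patient, on the day of the Randomization Visit (V1").

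The stated purpose of the windowing is "To maximize the data available for analysis". To that end, "results from ET and Unscheduled Visits will be allocated to scheduled visit according to the following rules and visit windows described in Table 2". If the scheduled visit already has a valid value, "then the value from the scheduled visit will be used in the analysis"; otherwise the early-termination (ET) or unscheduled value is taken for that visit.

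Table 2 opens the Randomization window at Day 1 and closes it at Day 12 (Group 1), Day 43 (Groups 2, 3 and 8), Day 64 (Groups 4 and 7) or Day 127 (Groups 6 and 9). Group 5 (DXA, MRI-PDFF, biopsy) has no Randomization window.

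Baseline is defined separately in SAP 7.1 as the "last scheduled or unscheduled value collected prior to the first dose of IMP treatment". For the MMRM, SAP 7.6.2.3 says: "All patients in the ITTS with non-missing baseline data and at least one post-baseline data are included in the analysis mode". SAP 7.6.2.4 counts a patient with no assessment at a visit as a non-responder for liver enzyme normalization.

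**The concern.** V1 is a pre-dose visit, but Table 2 gives it a window as if it were an ordinary visit with data on both sides. A result from Day 2 onward is post-baseline under SAP 7.1, yet Table 2 can label it Randomization. It is then set aside because a V1 value exists, and nothing in SAP sections 6 or 7 returns it to a post-baseline visit.

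The patients affected are those who leave early. Protocol Table 1 has no safety lab between V1 and Week 12, so for a patient who stops in the first six weeks the ET sample is the only planned post-dose lab. At stake is whether that sample appears in any laboratory summary by visit and whether the patient has a time point in the MMRM. A rule meant to keep data would here remove it.

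**Working it through.** **Reproducing the windows.** Target days (Protocol Table 1): V1 = 1, V2 = 22, V4 = 85, V5 = 127, V8 = 253. The upper bound is the midpoint of V1 and the next visit scheduled for that group. Days after Day 1 inside the window = bound − 1. The treatment period is 36 × 7 = 252 days. ET sampling is taken from Protocol Table 1 and section 7.4.

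| Group | Parameters | Midpoint | Table 2 bound | Days after Day 1 | Share of 252 days | Sampled at ET? |
|---|---|---|---|---|---|---|
| 1 | Vital signs, weight, edema, physical exam | (1+22)/2 = 11.5 | 12 | 11 | 4.4% | Yes |
| 2, 3, 8 | HbA1c; safety lab, FPG; metabolic parameters, insulin resistance indexes | (1+85)/2 = 43 | 43 | 42 | 16.7% | Yes |
| 4 | ECG | (1+127)/2 = 64 | 64 | 63 | 25% | Yes |
| 7 | Pregnancy test (women of child-bearing potential) | (1+127)/2 = 64 | 64 | 63 | 25% | Yes |
| 6, 9 | eGFR; fibrosis markers, biobanking | (1+253)/2 = 127 | 127 | 126 | 50% | No |

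Every Randomization bound reproduces (11.5 is rounded to 12). The arithmetic is right; the problem is using a midpoint for a visit that must be pre-dose. Midpoints were not used everywhere: the Group 5 Week 36 window opens on Day 79, which is the Week 12 target less its 6-day visit window (85 − 6).

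**Following one patient.** Take an ET visit on Day 35.

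- ALT, AST, FPG, HbA1c, insulin and lipids fall in Day 1 to 43, so they are allocated to Randomization.
- A valid V1 value exists, so the Day 35 value is not used.
- Nothing falls in the Week 12, 24 or 36 windows. The patient has no row in the by-visit change summaries, no time point in the MMRM, and is a non-responder for any enzyme raised at baseline.

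**Consistency across groups.** An ET visit on Day 60 is split three ways: vital signs go to Week 6 (34 to 64), labs to Week 12 (44 to 127) and ECG to Randomization (1 to 64).

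**Size.** Planned dropouts: 20% of 120 = 24. The documents give no timing. With an even spread over 252 days:

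- Group 1: 24 × 11/252 ≈ 1 patient
- Groups 2, 3 and 8: 24 × 42/252 = 4 patients
- Group 4: 24 × 63/252 = 6 patients

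If one third to one half of dropouts had their ET visit by Day 43, the lab figure would be 24/3 = 8 to 24/2 = 12. No such count applies to Groups 6 and 9, since neither eGFR nor fibrosis markers are scheduled at ET.

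**The case against.** The strongest case is that the outputs that matter most are protected, and that keeping off-time values out of a model by time point is sound. Most of this stands, and it rules out several stronger readings.

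- **Contaminated baseline.** A reader might infer this, the more so because SAP 7.6.2.3 puts V1 in brackets after the word baseline. SAP 7.1 excludes it: only a value before the first dose can be baseline. SAP 7.1 also gives table visit labels as week numbers and builds listings on nominal visit, so a mislabelled value would seldom be seen.
- **Affected primary endpoint.** Group 5 has no Randomization window, and ET MRI is planned only for withdrawal at or after Week 12.
- **Lost liver-safety signals.** The protocol does ask that "repeat testing should be performed within 48 to 72 hours" after a new elevation. With no safety lab scheduled between V1 and Week 12, an early repeat could only follow an unscheduled or ET test. TEAEs, including DILI as an event of special interest, are classified by date, and the listing of raised liver tests is not tied to a window.
- **All unscheduled tests in the first six weeks lost to the window.** For a patient who reaches Week 12, the priority given to the scheduled value would exclude them even if the window were moved.
- **ET results relabelled up to Day 127.** That bound touches unscheduled results only. These are also study days, so the bounds lie 11 to 126 days after the first dose.

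The objection also counts against one obvious remedy, which is to start the Week 12 or Week 36 window on Day 2. That would let a Day 3 HbA1c stand for Week 12 in the MMRM, or a Day 5 fibrosis marker for Week 36 in a regression without repeated measures.

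It does not justify calling a post-dose value Randomization, or dropping it from the safety summaries without saying so.

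**Conclusion.** The point holds as a minor defect. For patients whose ET visit falls by Day 43 (Day 64 for ECG, Day 12 for vital signs, weight and edema), the ET result does not reach the by-visit summaries. For labs it also does not reach the MMRM or the enzyme-normalization analysis; for weight it does not reach the weight MMRM in SAP 7.7.5.

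The size is about 4 patients for labs and 6 for ECG, across four arms. This rests on the planned 24 dropouts and an assumed even spread over 252 days; the lab figure rises to 8 to 12 if dropout is concentrated early. The planned total covers all sites, so counts in the main analysis sets, which exclude one site, could be lower. Only secondary, exploratory and descriptive safety outputs are involved.

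**What to change.** 1. In every group of Table 2, limit the Randomization window to Day 1 values taken before the first dose, with SAP 7.1's existing rule for missing times.
2. In the safety lab, vital sign, edema and ECG summaries, add an early on-treatment row for ET and unscheduled values that are post-dose but precede the first post-baseline window (before Day 13, 44 or 65, by group). State which value counts if a patient has several. Because an ET visit may be up to 8 days after the last dose, footnote the row accordingly.
3. Do not map values from Day 2 onward to Week 12 in the MMRM, or to Week 36 for eGFR and fibrosis markers. State that such values stay out of the MMRM and the enzyme-normalization analysis by choice, and report how many patients this concerns.

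The cost is an edit to one table, a small change to the windowing program and one sparse extra row per table. The early values become visible in the safety tables, but these patients still do not enter the MMRM.

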#### 5.8.2 *Procedure for withdrawal from the study*

**In the case of discontinuation of IMP for any reason listed in Section 5.8.1 *Criteria for withdrawal from the study* except SAE leading to death and lost to follow-up, patients will be asked to perform an Early Termination Visit within 8 days after the IMP discontinuation. At the Early Termination Visit, patients will be considered as withdrawn patients.** This visit will allow the Investigator to check the medical status of the patient and the patient to return all the IMP kits (used and unused), his/her patient diary and the self-monitoring blood glucose (SMBG) device for review if applicable. The SMBG device will be kept by the patient after the end of his/her study participation if applicable. The reason and date for withdrawal from the study must be documented in source documents, and reported in the eCRF and in the IWRS. If more than one reason of study withdrawal is given, the Investigator should make all efforts to establish the main reason.

If there is any medical reason for withdrawal from the study, the patient will remain under the supervision of the Investigator until resolution or stabilization of the medical condition. The Investigator must make every effort to collect the information related to the outcome of the event, as described in Section 8.3.8.5. This information is recorded in the part of eCRF dedicated to AEs. If the IMP is discontinued as a result of a SAE/AESI/Overdose/Pregnancy, the procedure described in Section 8.3.8.4 is to be implemented.

If patients are lost to follow-up, all reasonable means of contact must be used. In addition, a letter must be sent to the patient and a copy filed in the patient file (if allowed by site's Standard Operating Procedures). All the attempts (at least 3 by telephone by the Investigator or Clinical Research Coordinator (CRC) at study site) must be recorded in the patient file; last contact date will be reported in the eCRF.

Any withdrawal from the study, irrespective of the reason, is to be notified immediately to the Medical Monitor and POXEL Medical Representative.

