7.7.8 Pitting Edema

Shift tables from baseline will be presented at each post-baseline visit showing the number of patients per treatment group with each populated grade for the Safety set.

A listing will also be provided for the Safety set with site 065-S .

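### SAP 6.1 leaves an Early Termination or unscheduled result out of the by-visit tables and the MMRM when that window's scheduled visit has a valid value, and no other table of measured values picks it up

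*SAP*

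**What the plan says.** SAP 6.1 opens with its purpose: "To maximize the data available for analysis, where possible, results from ET and Unscheduled Visits will be allocated to scheduled visit". It then ranks the sources. "If a valid value exists for the scheduled visit to which the ET/Unscheduled Visit has been allocated then the value from the scheduled visit" is the one analysed; "otherwise the values from the ET/Unscheduled Visits will be used in the analysis for the particular scheduled visit".

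Table 1 of that section puts "Pitting edema assessment, vital signs and body measurements, physical examination" in Group 1, with windows around every visit. It puts "Safety lab, FPG" in Group 3, with windows only around Screening, V1, Week 12, Week 24, Week 36 and Week 38. In Table 2 the Week 12 window is Days 65-106 for Group 1 and Days 44-127 for Group 3.

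The outputs follow analysis visits. SAP 7.1 presents tables by analysis visit and uses an Early Termination label only in listings. SAP 7.7.3 summarises laboratory data by scheduled visit. For edema, SAP 7.7.8 states: "Shift tables from baseline will be presented at each post-baseline visit". The MMRM of SAP 7.6.2.3, "which uses values at all time points with data available", covers liver enzymes, glycemic parameters and insulin resistance indexes. SAP 7.6.3 extends it to lipids, adiponectin and hsCRP, and SAP 7.7.5 to weight.

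On timing, Protocol 5.8.2 says "patients will be asked to perform an Early Termination Visit within 8 days after the IMP discontinuation". The patient then counts as withdrawn, so no later scheduled visit is planned.

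**The concern.** The ET visit is the measurement closest to the decision to stop. A patient seen at Week 12 on Day 85 with an ET visit on Day 100 has the ET weight, edema grade and laboratory results all allocated to Week 12, where the Day 85 values displace them. No later visit replaces them.

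This matters most where the measured quantity could be tied to withdrawal. Protocol 4.2 uses weight to test whether the drug avoids the gain seen with pioglitazone. Protocol 8.3.8.1.4 makes pitting edema an event of special interest and sets liver-test levels at which drug is stopped. That section also calls for repeat liver tests within 48 to 72 hours and, under close observation, two or three times weekly. These are unscheduled results, and a peak among them can be displaced in the same way.

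The SAP also treats the same ET visit in two ways. A liver-fat scan from Day 79 on fills Week 36, while the weight and ALT taken alongside it may enter no table.

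**Working it through.** **Inputs from the documents.** Visit days 1, 22, 43, 85, 127, 169, 211, 253, 267 and the windows (SAP Table 2); ET within 8 days of stopping study drug (Protocol 5.8.2 and 7.4); 20% dropout of 120 patients (SAP 2.3).

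**Assumptions, not in the documents.** Stop days evenly spread; delay L to ET evenly spread over 0 to 8 days; visits due after the stop are not attended.

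**Table 2 reproduced.** The limits are midpoints of adjacent visit days. Group 1: (43+85)/2 = 64, (85+127)/2 = 106, (127+169)/2 = 148. Group 3: (1+85)/2 = 43, (85+169)/2 = 127, (169+253)/2 = 211, (253+267)/2 = 260. All match.

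**Share left out, stop from Day 85, ET by Day 252.** A result is left out when the window's visit took place on or before the stop day and ET comes later in that window. For L of 1 or more there are 168 − L possible stop days.

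- Weight and edema: four visits (Days 85, 127, 169, 211), each window ending 21 days after its visit. Left out = 4 × (22 − L).
- Laboratory: two visits (Days 85, 169), each window ending 42 days after its visit. Left out = 2 × (43 − L).

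| Delay L | Weight/edema | Laboratory |
|---|---|---|
| 0 or 1 day | 84/167 = 50.3% | 84/167 = 50.3% |
| 4 days | 72/164 = 43.9% | 78/164 = 47.6% |
| 8 days | 56/160 = 35.0% | 70/160 = 43.8% |
| Mean over 0-8 | 43.6% | 47.4% |

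If the ET visits on Days 253-260 are also counted (stops up to Day 252), they fill Week 36 and none is lost. The shares become 644/1512 = 42.6% and 700/1512 = 46.3%. Simulation with visits varying within their ±4 or ±6 day windows gives 42.9% and 46.4%. Hence about 43% and 46-47%.

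**Sensitivity.** If withdrawals cluster early (assumed exponential, mean 60 days after Day 85), the shares are 48.6% and 60.0%. With the fixed 8-day delay, weight and edema fall to 35.0%. This gives the range of about 35-60%, which is not a bound. If drug is stopped at a visit before Week 36 that collects the parameter and ET is a separate visit 1-8 days later, every such result is left out. If every ET falls past the midpoint and before the next visit, none is.

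**Patients.** 20% of 120 = 24. Over all ET days 2-252 the shares are 42.4% and 47.0%: 24 × 0.424 = 10.2 and 24 × 0.470 = 11.3, or about 2.5 and 2.8 per arm. These include ET results in the Randomization window (Days 1-12 for weight, 1-43 for laboratory), where the V1 value wins. Counting post-randomization windows only, the shares are 39% and 31%, or about 9 and 7 patients.

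**The case against.** Preferring the scheduled value is an ordinary windowing convention, and the kept value is closer to the nominal day. The stated aim of using more data is qualified, and the rule does fill empty visits. It is therefore not a contradiction, though it recovers less than its introduction suggests.

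A reader might call the omitted result the last on-treatment value. That is not safe, because ET may come up to 8 days after the last dose.

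A reader might also infer that the safety information disappears. It does not. Listings keep every value. The protocol requires an abnormal finding that leads to discontinuation to be reported as an adverse event, and edema and confirmed drug-induced liver injury are events of special interest. SAP 7.7.2 tabulates both routes and counts events up to 7 days after discontinuation as treatment-emergent. SAP 7.7.3.1 lists ALT, AST, bilirubin and ALP beyond the predefined limits of change (PDLC). These routes cover what the investigator judges significant, and the PDLC output is only a listing. None of them summarises measured weight, edema grade or laboratory values.

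For the MMRM, edema is in no such model, and affected patients still contribute their attended visits. It is not shown that the omitted value decides whether missing-at-random is tenable.

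Moving the ET value to the next unattended visit is also open to objection. A Day 86 laboratory result would be labelled Week 24 (169 − 86 = 83 days later), although SAP 7.6.2.3 uses observed data only. That objection stands, and the fix avoids the move.

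**Conclusion.** The point holds as a gap in the summaries. Followed exactly, SAP 6.1 leaves these ET and unscheduled results out of the by-visit tables and, for parameters modelled there, out of the MMRM. No other table of measured values includes them.

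The size depends on assumptions. It is about 43% for weight and edema and 46-47% for laboratory results if withdrawals from Day 85 are evenly spread with a 0-8 day delay, and plausibly 35-60%. A reader might take one percentage as a consequence of the SAP, but the documents give neither timing nor delay. The 10-11 patients are an upper figure under even timing, because Protocol 5.8.2 exempts deaths and patients lost to follow-up from the ET visit.

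A reader might also infer that the safety tables will look better than the data. The documents show no direction of bias, so this remains a risk. The primary endpoint is untouched: there is no scheduled scan between Screening and Week 36, and an ET scan from Day 79 fills Week 36. This is a cheap improvement to the safety reporting of small arms and does not put the trial's main conclusion in doubt.

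**What to change.** Keep the by-visit rule in SAP 6.1 and add to the safety outputs:

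- SAP 7.7.3.1 and 7.7.5: a row for the last post-baseline value, including ET, for laboratory parameters and weight.
- SAP 7.7.8: a shift from baseline to worst post-baseline edema grade, using all scheduled, ET and unscheduled assessments.
- SAP 7.7.3.1: a table of maximum post-baseline ALT, AST, bilirubin and ALP against the existing PDLC limits, from the same three sources.

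Do not reallocate ET values to a later planned visit.

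The cost is a short derivation and a few table rows. Some values will have been taken up to 8 days after the last dose, so flag them and footnote the delay.
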